### **14. Biostatistics:**

**Power & Sample Size Estimation:** The sample size for the study was designed to achieve 85% power when comparing the change in the actively treated group to the change in the sham treated group, using assumed rates of 50% and 10% improvement, respectively. A two-sided test of results in evaluable subjects (qualified for analyses of efficacy on vibration perception threshold and on structured S-W monofilament testing) will provide the specified power at a 5% significance level. Sample size calculations resulted in a requirement for a total of twenty-seven (27) subjects in each group. The sample size was also estimated using our pilot data in which we explored the benefit of plantar stimulation for improving balance (Study 5). At baseline, the area of sway for center of mass (COM) was  $5.23 \pm 2.81 \text{ cm}^2$  and  $5.41 \pm 1.14 \text{ cm}^2$  respectively for the sham and intervention groups. After week two of treatment, the area of COM sway was  $4.94 \pm 3.42 \text{ cm}^2$  for the sham and  $3.49 \pm 1.25 \text{ cm}^2$  for the intervention group. Using the same criteria explained above, to observe a significant improvement in the intervention group receiving active stimulation compared to sham group (with nonfunctional stimulator), twenty seven subjects per group is required. Assuming 10% drop out, therefore, 40 subjects per group (a total of 80 subjects) should be enough for the purpose of this study.

No suitable alternative treatments exist for patients with loss of protective sensation due to diabetic peripheral neuropathy, so a statistically detected difference in improvement between groups may be considered a clinically meaningful result. However, the study was designed to detect a sufficiently large difference to account for an anticipated “placebo effect” in the sham treated group.

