### **Analysis Plan:**

P-values of 0.05 or less will be considered statistically significant based on a two-sided test unless otherwise noted. All variables will be tabulated descriptively at each scheduled time point. For each continuous variable, the analyses will include the mean, standard deviation, minimum and maximum. For each categorical variable, the summary will include frequencies and percentages. Each variable will be analyzed using all available data. Baseline variables will be summarized using descriptive statistics. Between-group differences for primary and secondary endpoints will be explored at the time of the last treatment visit (weeks 12) and every two weeks of treatment.

Additionally, the retention of potential benefit will be assessed at the time of follow-up visit following the completion of treatment (two weeks post termination of treatment). The frequency of subjects

with adverse events (AEs) will be tabulated. AEs will also be tabulated by severity and, when appropriate, by relationship to study treatment. The difference in the occurrence of adverse events between the study groups will be compared descriptively.

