To determine whether gait, balance, and physical activity variables change significantly across different study visit epochs, within-subject analyses of variance (ANOVA's) will be employed. We assume that plantar electrical stimulation is helpful to improve subjects gait, balance, and physical activity. Then sensor-derived movement variables should change substantially from baseline to the end of the study for the active group with no significant change in placebo group. For example, the range of motion of COM and RCI values should be reduced and gait velocity should be increased. Next, for all continuous variables, pretreatment scores will be regressed on post-treatment scores to form residualized change scores (e.g. VPT, monofilament test, pain intensity, A1C, etc). Correlations will then be generated among these scores to determine whether changes in sensor-derived movement factors are related appropriately with increases in (clinically assessed) functional capacities and self-report measures of activities, mood, socializing, etc. ANOVA test will be used to examine significant difference between intervention and sham group at baseline for age and BMI as well as the indicated outcomes (e.g. gait, balance, VPT, ABI,. Etc). We assumed there is no significant difference between sham and intervention group at baseline for the indicated variables. The same test will be repeated for the week 12. We assumed that the outcomes of study will be improved in the intervention group compared to the sham group. Paired- sample t-test will be used to examine the retention of the electrical stimulation therapy at two weeks post stopping the therapy compared to week-12. We assumed the benefit of the electrical stimulation therapy will be retained at least for two weeks. Additional analyses will examine the degree to which early-treatment changes in cognitive variables and functional capacity variables (representing functional restoration processes) predict late-treatment changes in moving ability post plantar electrical stimulation therapy. Such analyses will also allows to elucidate the relative contributions fear of falling (assessed using FES score); and/or and range of motion (assessed using body worn sensors) made to bringing about clinically meaningful changes in gait balance control. Moderator effects will also be examined for exploratory purposes. Using gender as an example, mixed design ANOVA's will be conducted to determine whether gait and balance factors change over the course of treatment at different rates or with different patterns for men and women as well as for patients with high or low severity of neuropathy and peripheral vascular disease. We assume those who have higher peripheral vascular problem will receive maximum benefit from electrical stimulation. Additional analyses will test whether changes in gait and balance variables predict changes in clinically important outcome factors (e.g., fear of falling (FES) , quality of life (SF12), adverse events, foot ulcer, etc) depending on gender.

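### Section 14 attaches 85% power at 27 per group to two calculations, and neither establishes that power for a test in the Analysis Plan

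*Combined protocol and SAP*

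**What the plan says.** In the Combined protocol and SAP, section 14 (Power & Sample Size Estimation) opens with "The sample size for the study was designed to achieve 85% power" for the contrast of active and sham, "using assumed rates of 50% and 10% improvement, respectively". The population and endpoints follow: "A two-sided test of results in evaluable subjects (qualified for analyses of efficacy on vibration perception threshold and on structured S-W monofilament testing"), which "will provide the specified power at a 5% significance level". The result is stated as "Sample size calculations resulted in a requirement for a total of twenty-seven (27) subjects in each group".

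The same paragraph makes a second calculation: "The sample size was also estimated using our pilot data in which we explored the benefit of plantar stimulation for improving balance". It prints COM sway means and SDs by arm at baseline and at treatment week 2, applies the same power and significance level, and again arrives at 27 per group. With 10% loss, enrolment is set at 40 per group.

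The Analysis Plan, also in section 14, treats categorical data descriptively: "For each categorical variable, the summary will include frequencies and percentages". It says that between-group differences on primary and secondary endpoints will be explored, without naming a test at that point. The between-group test it does name is ANOVA, listed at baseline for outcomes that include gait, balance and VPT, and then "The same test will be repeated for the week 12". VPT and monofilament results also enter as continuous residualized change scores, which feed correlations.

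**The concern.** A power figure describes one test on one outcome under one set of assumptions. Here the rates that set the 85% look like proportions of patients who improve in sensation. The plan analyses VPT as a continuous measure, and H1 to H6 cover balance, gait, perfusion, quality of life, activity and falls. The sway calculation does match a planned comparison, so its 27 has to carry the claim, and that depends on whether it follows from the printed values.

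What is at stake is how the results are read. If the ANOVA on VPT or sway finds no difference, a reader who relies on section 14 would take it as a null result from a comparison with 85% power. The documents do not support that reading for either outcome.

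**Working it through.** **1. The 50% v 10% calculation.** Inputs (section 14): p₁ = 0.50, p₂ = 0.10, two-sided 5% (z = 1.960), 85% power (z = 1.036). The mean proportion is 0.30.

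- Uncorrected: n = [1.960·√(2·0.30·0.70) + 1.036·√(0.50·0.50 + 0.10·0.90)]² / 0.40² = 21.96, so 22.
- Continuity-corrected: n = (21.96/4)·[1 + √(1 + 4/(21.96·0.40))]² = 26.73, so **27**, the stated figure.

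The alternative reading, a 40-point difference in mean percent improvement, has no printed SD. With 27 per group, 85% power needs a difference of 0.83 SD, so the SD would have to be about 40/0.831 = 48 points.

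**2. Is that test planned?** The plan gives no definition of improvement on VPT or monofilament and names no test of proportions. Its named between-group test is ANOVA, and its list names VPT. For VPT as a continuous measure no SD is printed, so its power cannot be computed.

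**3. The COM sway calculation, week-2 values.** Inputs (section 14): sham 4.94 (SD 3.42), intervention 3.49 (SD 1.25) cm².

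- Difference: 4.94 − 3.49 = 1.45 cm².
- Pooled SD: √[(3.42² + 1.25²)/2] = 2.57 cm².
- Standardized difference: 1.45/2.57 = 0.56.

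Two-group ANOVA is equivalent to the equal-variance t-test. With noncentrality 0.563·√(n/2) and 2n − 2 degrees of freedom:

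| Per group | Power |
|---|---|
| 27 | 53% |
| 36 (40 less 10%) | 65% |
| 40 | 70% |

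For 85% power, 57.6 per group are needed, so 58. The normal approximation, (3.42² + 1.25²)·(2.996/1.45)² = 56.6, gives 57. Allowing for unequal variances gives 52% at 27 and 65% at 36.

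**4. The COM sway calculation, change scores.** Add the baseline values: sham 5.23 (SD 2.81), intervention 5.41 (SD 1.14).

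- Difference in change: (5.41 − 3.49) − (5.23 − 4.94) = 1.92 − 0.29 = 1.63 cm².
- Variance of change in each arm: s₀² + s₂² − 2·r·s₀·s₂, where r is the baseline-to-week-2 correlation. The documents do not give r, so it is assumed here to be the same in both arms.
- n per group = (sum of the two variances)·(2.996/1.63)².

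| Assumed r | n per group for 85% |
|---|---|
| 0 | 76 |
| 0.5 | 39 |
| 0.6 | 32 |
| 0.7 | 24 |

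The stated 27 requires r of about 0.66.

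**5. What the planned size does support.** For a difference in means at two-sided 5%, 85% power is reached at 0.83 SD with 27 per group and at 0.72 SD with 36 per group.

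**The case against.** The strongest reply is that section 14 does tie 85% to a planned comparison. Balance is H1, COM sway is its measure, and ANOVA compares it between arms. That stands, so a reader who infers that section 14 links its power to no planned outcome goes too far. What fails is the derivation: the printed values give 27 only on change scores with a correlation that is never stated.

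Second, the proportions reading is an inference. Section 14 speaks of comparing change and never mentions responders or a continuity correction. This also stands. The exact match at 27, and the absence of any SD, make proportions the better reading, but the mean-percent reading cannot be ruled out. It would leave the calculation resting on an unstated SD.

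Third, the mismatch may do no harm. If 50% v 10% came from a normal measure with equal spread in both arms, the underlying shift would be 1.28 SD, and ANOVA with 27 per group would have over 99% power. So the documents do not support inferring that the VPT comparison is underpowered; its power is simply unknown.

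Finally, the sentence on categorical variables concerns descriptive summaries, and the plan leaves room for unnamed between-group tests. It therefore does not forbid a test of proportions, but it does not specify one either.

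**Conclusion.** The concern holds in this form: neither calculation establishes 85% power for a test that the plan specifies. The responder-type calculation is arithmetically sound but has no matching definition, named test or hypothesis. The sway calculation has a matching outcome, but on observed week-2 values it supports about 53% power at 27 per group and 65% at 36, with about 58 needed for 85%.

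These sway figures assume that the week-2 pilot means and SDs carry over to the end-of-treatment visit, which the Analysis Plan places at week 12. The pilot in Study 5 assessed postural control in thirteen subjects, so its SDs are imprecise.

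A reader might go on to infer that the trial is too small for balance. The documents do not show that. If change scores are intended and r is 0.7, 24 per group suffice; at r = 0.5, 39 are needed. The defect lies in the stated justification, and the adequacy of 40 per group is left open.

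**What to change.** In section 14:

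1. Remove the 50% and 10% rates as the basis of the 85%. Adding a responder test to rescue them is not advised, because it would concern an outcome outside H1 to H6.
2. State that with 36 evaluable per arm (40 × 0.90) the planned between-group ANOVA has 85% power at two-sided 5% for a 0.72 SD difference in means.
3. For COM sway, state that the pilot week-2 values (about 0.56 SD) imply about 65% power at 36 per arm. If change scores are the intended analysis, say so in the Analysis Plan, and give the assumed correlation and the resulting power.

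The cost is a few sentences and no extra patients. The downside is that the stated power for balance will look less favourable.

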### **Analysis Plan:**

P-values of 0.05 or less will be considered statistically significant based on a two-sided test unless otherwise noted. All variables will be tabulated descriptively at each scheduled time point. For each continuous variable, the analyses will include the mean, standard deviation, minimum and maximum. For each categorical variable, the summary will include frequencies and percentages. Each variable will be analyzed using all available data. Baseline variables will be summarized using descriptive statistics. Between-group differences for primary and secondary endpoints will be explored at the time of the last treatment visit (weeks 12) and every two weeks of treatment.

Additionally, the retention of potential benefit will be assessed at the time of follow-up visit following the completion of treatment (two weeks post termination of treatment). The frequency of subjects

with adverse events (AEs) will be tabulated. AEs will also be tabulated by severity and, when appropriate, by relationship to study treatment. The difference in the occurrence of adverse events between the study groups will be compared descriptively.

To determine whether gait, balance, and physical activity variables change significantly across different study visit epochs, within-subject analyses of variance (ANOVA's) will be employed. We assume that plantar electrical stimulation is helpful to improve subjects gait, balance, and physical activity. Then sensor-derived movement variables should change substantially from baseline to the end of the study for the active group with no significant change in placebo group. For example, the range of motion of COM and RCI values should be reduced and gait velocity should be increased. Next, for all continuous variables, pretreatment scores will be regressed on post-treatment scores to form residualized change scores (e.g. VPT, monofilament test, pain intensity, A1C, etc). Correlations will then be generated among these scores to determine whether changes in sensor-derived movement factors are related appropriately with increases in (clinically assessed) functional capacities and self-report measures of activities, mood, socializing, etc. ANOVA test will be used to examine significant difference between intervention and sham group at baseline for age and BMI as well as the indicated outcomes (e.g. gait, balance, VPT, ABI,. Etc). We assumed there is no significant difference between sham and intervention group at baseline for the indicated variables. The same test will be repeated for the week 12. We assumed that the outcomes of study will be improved in the intervention group compared to the sham group. Paired- sample t-test will be used to examine the retention of the electrical stimulation therapy at two weeks post stopping the therapy compared to week-12. We assumed the benefit of the electrical stimulation therapy will be retained at least for two weeks. Additional analyses will examine the degree to which early-treatment changes in cognitive variables and functional capacity variables (representing functional restoration processes) predict late-treatment changes in moving ability post plantar electrical stimulation therapy. Such analyses will also allows to elucidate the relative contributions fear of falling (assessed using FES score); and/or and range of motion (assessed using body worn sensors) made to bringing about clinically meaningful changes in gait balance control. Moderator effects will also be examined for exploratory purposes. Using gender as an example, mixed design ANOVA's will be conducted to determine whether gait and balance factors change over the course of treatment at different rates or with different patterns for men and women as well as for patients with high or low severity of neuropathy and peripheral vascular disease. We assume those who have higher peripheral vascular problem will receive maximum benefit from electrical stimulation. Additional analyses will test whether changes in gait and balance variables predict changes in clinically important outcome factors (e.g., fear of falling (FES) , quality of life (SF12), adverse events, foot ulcer, etc) depending on gender.

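### Within-subject ANOVA across visits and an unadjusted week-12 test, with no analysis set or missing-visit rule, do not secure the promised use of all available data

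*Combined protocol and SAP*

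**What the plan says.** All of the analysis text is in Section 14 (Biostatistics).

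- **Data used.** The Analysis Plan states: "Each variable will be analyzed using all available data".
- **Change over visits.** For gait, balance and activity measures, "within-subject analyses of variance (ANOVA's) will be employed". The plan expects substantial change from baseline in the active group and no significant change in the placebo group.
- **Arm comparison.** A separate ANOVA compares intervention with sham at baseline and is repeated at week 12. The plan also mentions looking at arm differences every two weeks. No baseline covariate is named. Residualised change scores are described, but they feed correlations and not the arm comparison.
- **Retention.** A paired t-test compares week 12 with two weeks after stopping.
- **Power.** The paragraph on sample size refers to "A two-sided test of results in evaluable subjects (qualified for analyses of efficacy on vibration perception threshold" (and on monofilament testing). No rule says who qualifies.
- **Drop-out.** "Assuming 10% drop out, therefore, 40 subjects per group (a total of 80 subjects) should be enough".

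Section 14 nowhere says that all randomised patients are analysed as assigned, and it gives no method for missing visits.

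**The concern.** The stated aim is to use every observation, but the method named for the main movement outcomes does not naturally do so. Classical repeated-measures ANOVA needs a value at each visit entered, so a patient with one missed visit contributes nothing unless some other handling is specified, and none is. Patients who miss visits in a 12-week device study may differ in adherence, discomfort or falls, so completers need not represent the randomised groups.

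Two further weaknesses bear on the treatment conclusion. First, significant change in one arm and non-significant change in the other is not a test of the difference between arms. Second, the test that does compare arms uses week-12 values alone and ignores baseline measurements that are already collected. The sample size, by contrast, is framed as a comparison of change between the groups.

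The undefined evaluable group leaves open which patients count for efficacy. That should be settled before the data are unblinded.

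**Working it through.** **1. The plan's own figure.** The inputs, all from Section 14, are: "using assumed rates of 50% and 10% improvement, respectively" (active and sham), 85% power and a two-sided 5% level. The normal approximation with pooled variance under the null gives

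n = [1.960 × √(2 × 0.3 × 0.7) + 1.036 × √(0.5 × 0.5 + 0.1 × 0.9)]² / 0.4² = (1.270 + 0.604)² / 0.16 ≈ 22.

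With the continuity correction, using the unrounded 21.96,

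n′ = (21.96 / 4) × [1 + √(1 + 4 / (21.96 × 0.4))]² ≈ 26.7, rounded up to 27.

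This matches "Sample size calculations resulted in a requirement for a total of twenty-seven (27) subjects in each group". Allowing for 10% drop-out gives 27 / 0.9 = 30. The plan enrols 40, which leaves 40 × 0.9 = 36. Up to 1 − 27/40 = 32.5% of a group could be lost before its number falls below 27.

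**2. Which analysis needs which data.**

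| Analysis | Data a patient must have |
|---|---|
| Within-subject ANOVA across visits (classical form) | every visit entered |
| ANOVA between arms at week 12 | week 12 only |
| Paired t-test for retention | week 12 and the retention visit |
| Power statement | undefined evaluable status |

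An intermediate missed visit affects only the first row.

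**3. Number of visits.** Section 4 gives five visits: baseline and weeks 2, 4, 6 and 8, the last being two weeks after treatment. Section 1 and the Analysis Plan describe 12 weeks of treatment. With two-weekly visits and a retention visit that makes eight (baseline, six during treatment, one after). Activity is a special case: Table IV schedules it at baseline and week 6 only, while the text under Hypothesis 5 has it at every study visit.

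**4. Illustration of complete-case loss.** The documents give no missed-visit rate. Let m be an assumed rate per post-baseline visit, independent across visits. Starting from 36 per group, complete cases = 36 × (1 − m)^(visits − 1).

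| m | 5 visits | 8 visits |
|---|---|---|
| 2% | 33.2 | 31.3 |
| 5% | 29.3 | 25.1 |
| 10% | 23.6 | 17.2 |

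Complete cases reach 27 when m = 1 − (27/36)^(1/4) = 6.9% over five visits, or 1 − (27/36)^(1/7) = 4.0% over eight.

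These counts are on the pessimistic side. Missed visits that cluster within patients leave more complete cases. Drop-outs also generate missed visits, so taking 10% off first may count some patients twice. If the retention visit is left out because it has its own t-test, m = 5% leaves 36 × 0.95³ = 30.9 on the Section 4 schedule. Activity measured at only two time points would lose least.

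**The case against.** A reader might infer that the plan drops every patient with a missed visit, that its treatment comparison is therefore made in completers, and that the protection of randomisation is lost. The documents do not support that.

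- Nothing in Section 14 says that patients are excluded for a missed visit. Deletion is how the classical method usually behaves, and the plan is silent on handling.
- The described arm comparison is a single-visit ANOVA. It loses patients absent at week 12 and nobody for an intermediate miss, and using the data available for each variable is compatible with it.
- Evaluable appears only in the power paragraph. Sizing a trial on patients with outcome data and then inflating for drop-out is ordinary practice, and nothing declares that group to be the efficacy population.
- Enrolling 40 against a stated need of 27 absorbs moderate loss.

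All of this stands, and it limits the point to an unspecified analysis with a risk attached. It does not remove the point. The plan reads treatment benefit partly from the within-subject ANOVA, so the patients who enter it matter. The single-visit test still leaves baseline values unused. An undefined efficacy qualification also remains open to definition after randomisation, for example by device use, which is recorded.

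**Conclusion.** The concern holds as a gap in specification and a weak choice of method. The within-subject ANOVA does not deliver the promised use of the data unless missing visits are handled in some stated way. The week-12 ANOVA is unadjusted for baseline. Neither the analysis population nor evaluable status is defined.

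No bias and no loss of power is demonstrated. It is tempting to turn the complete-case counts into a power figure for the arm comparison, but that would apply a two-sample test to numbers that arise only in the within-subject analysis, using a miss rate the documents do not give. The counts show only that the plan's margin could be used up in that analysis at a missed-visit rate of about 7% (five visits) or 4% (eight visits), assuming independent misses after 10% drop-out. Whether the pilot sway data support 27 per group is a separate question, not addressed here.

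The change is worth making before unblinding. It does not require a different trial.

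**What to change.** 1. **Reconcile the visit schedule first.** Section 4 (weeks 2, 4, 6 and 8) and the 12-week treatment period in Section 1 and the Analysis Plan must agree, because the main contrast depends on which visit is the last on treatment. The timing of activity monitoring also needs to agree between Table IV and the Hypothesis 5 text.
2. **Outcomes measured at repeated visits.** Replace the within-subject ANOVA and the unadjusted week-12 ANOVA with a mixed model for repeated measures: arm, visit, arm-by-visit and baseline value, in all randomised patients as assigned. The main contrast is the arm difference at the last treatment visit.
3. **Outcomes with one follow-up** (SF-12, and activity if Table IV stands). Use ANCOVA on the baseline value.
4. **Evaluable subjects.** Define the term or delete it from the power paragraph, and keep an allowance for missing outcomes in the sample size.
5. **Sensitivity analysis.** Add one for data not missing at random, since discomfort, adherence and falls are plausible reasons for absence.

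The cost is analysis-plan wording and slightly more analysis work in standard software, with no new data collection. The main model relies on data being missing at random, which is why item 5 is needed. Patients with no post-baseline value add nothing to the arm contrast, so follow-up of those who stop using the device still matters.

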**Sponsor:**

**Qatar National Priority Research Program**

**NPRP No.: NPRP 5 - 117 - 3 - 028**

## **1. Introduction and Purpose:**

Our long-term goal is to provide a convenient, low-cost therapeutic device and treatment protocol for diabetic patients with high risk of falling. Eventually, we plan for this to be an approach that can be used by patients at home. We will use preliminary data from this study to plan and implement a randomized clinical study in high risk diabetics to evaluate long-term clinical outcomes, specifically a reduction of falls, foot ulcers and amputations in patients that use the electrical stimulation treatment.

This study will be a double-blind randomized clinical trial design consisting of two groups of forty (40) patients with diabetic peripheral neuropathy and some level of postural instability. The study consists of a 12 weeks treatment phase and two weeks of retention. Subjects will be asked to wear a comfortable electrical stimulation device (SENSUS™ Pain Management System, Neurometrix, Inc., Waltham, MA) during night time on daily basis for duration of 8 hours. The proposed dosage regimen was used in our preliminary studies and no related adverse event was reported while a significant improvement in skin perfusion was observed. The objective of this proposed study is threefold:

**Aim1:** To compare postural control in subjects assigned to use the active Electrical Stimulation (intervention group) and subjects assigned to non-functional stimulator (sham group). Balance will be assessed for both groups at baseline and at monthly intervals. Study hypotheses are:

**H1:** Electrical Stimulation will improve postural coordination and helps to reduce body sway during standing in the treatment group compared to the sham group as well as compared to the baseline.

**H2:** Electrical Stimulation will improve gait, gait initiation, and gait inter-cycle variability compared to the sham group as well as compared to the baseline.

**Aim2:** To compare changes in skin perfusion in patients treated with Electrical Stimulation compared to sham therapy.

**H3:** Electrical Stimulation will improve dorsal and plantar perfusion compared to the control group and compared to baseline.

**Aim3:** To evaluate changes in quality of life in high risk diabetes who received Electrical Stimulation compared to sham therapy.

**H4:** Plantar stimulation will improve subject quality of life in the intervention group assessed using SF36.

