#### **4. Study Procedures:**

There will be a total of five study visits required for each patient. There will be one scheduled visit for baseline evaluation and four additional visits at 2 weeks, 4 weeks, 6 weeks during treatment and 8 weeks (2 weeks post stopping the treatment). The baseline visit will involve completion of a standardized intake form, which will include pertinent demographics such as age, height, weight, education level, occupation, and comorbidities of the study patient (see Table IV). Several clinical assessments will be performed at baseline as well as at each study visit to evaluate severity of neuropathy and skin perfusion as described in the table IV.

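### The protocol states two treatment durations: Section 14 sets the end-of-treatment and retention tests at week 12, but the visit schedule ends treatment at week 6

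*Combined protocol and SAP*

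**What the plan says.** **12-week text.** Section 1 states: "The study consists of a 12 weeks treatment phase and two weeks of retention". The device is worn "during night time on daily basis for duration of 8 hours". Under Aim 1, the same section adds: "Balance will be assessed for both groups at baseline and at monthly intervals". The Analysis Plan of Section 14 takes up "Between-group differences for primary and secondary endpoints" and says that these "will be explored at the time of the last treatment visit (weeks 12) and every two weeks of treatment". After describing the baseline ANOVA between groups, the plan continues: "The same test will be repeated for the week 12". The retention paired t-test looks at outcomes "at two weeks post stopping the therapy compared to week-12".

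**6-week text.** Section 4 states: "There will be a total of five study visits required for each patient". It lists them as baseline, weeks 2, 4 and 6 during treatment, and week 8, which it defines as two weeks after treatment stops. Table IV gives the same follow-up weeks. Table IV and Hypothesis 4 (Specific Aim 3) put the follow-up SF-12 at week 6, and Specific Aim 1 has balance measured bi-weekly rather than monthly.

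**Other timing statements.** The fall log in Table IV refers to a study period of 4 weeks. Activity monitoring is at baseline and week 6 in Table IV, but at every study visit under Hypothesis 5.

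**The concern.** The comparison with sham at the end of treatment is the plan's main efficacy contrast, and the paired t-test is its only named test of retention. Both are tied to a week that the visit schedule does not contain. If this is left open, someone must choose the analysis week later, possibly after seeing data from weeks 2, 4, 6 and 8.

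The conflict also reaches beyond these two tests. Week 8 is an off-treatment visit in Section 4, but it falls inside the treatment phase of Section 1. Any analysis that depends on when treatment ends changes meaning with the duration: the within-subject ANOVAs across visits, the residualized change scores built on post-treatment values, and the prediction of late-treatment changes. Recruitment is planned at two centers (Section 3). If one followed Section 1 and the other Section 4, their week-8 data would not measure the same thing.

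**Working it through.** **1. The stated analysis time against the schedule.** The plan's own figure is week 12 for the last treatment visit.

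| | Sections 1 and 14 | Section 4 and Table IV |
|---|---|---|
| Treatment phase | 12 weeks | 6 weeks |
| Last on-treatment visit | week 12 | week 6 |
| Retention visit | 12 + 2 = week 14 (inferred; not named) | 6 + 2 = week 8 |
| Status of week 8 | on treatment | off treatment |
| Balance assessments | monthly (Section 1) | every two weeks |

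The visits in Section 4 are {0, 2, 4, 6, 8}. Neither 12 nor 14 is in that set. The visit window in Table IV is +2 days, so the last visit can fall no later than day 8 × 7 + 2 = 58. Week 12 is day 12 × 7 = 84.

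**2. Planned stimulation at 8 hours every night.**

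- 6 weeks: 6 × 7 × 8 = 336 hours
- 12 weeks: 12 × 7 × 8 = 672 hours
- Ratio: 672 / 336 = 2

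**3. Which outcomes support a week 8 v week 6 test under the operational schedule.**

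| Outcome | Scheduled weeks | Retention test possible? |
|---|---|---|
| Balance, gait, neuropathy, pain VAS, vascular measures | 0, 2, 4, 6, 8 | yes |
| SF-12 | 0, 6 | no |
| Activity monitoring, Table IV | 0, 6 | no |
| Activity monitoring, Hypothesis 5 | every visit | yes |

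Replacing 12 by 6 in Section 14 is therefore not quite enough. The retention test also needs its outcomes named.

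**4. Sample size.** The 27 per group reproduces from 50% v 10%, 85% power and a two-sided 5% level with the continuity-corrected two-proportion formula (22 without the correction). None of these inputs involves treatment duration. The second justification in Section 14 uses pilot sway data at week two. The sample size does not depend on which duration is right.

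**The case against.** The best defense is that the intent can be recovered. Section 14 names the time points by function as well as by number: the final visit on treatment, and the visit two weeks after treatment ends. Under Section 4 these are weeks 6 and 8. The plan also analyzes whatever data are available. This stands in part. A reader might infer that the two tests are impossible. The documents do not support that: once the duration is fixed, both can be run, at least for outcomes measured at the visits concerned.

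A reader might also infer that the protocol nowhere provides for a week-12 assessment. That goes too far. Monthly balance assessments over the 12-week phase in Section 1 imply one. The absence of week-12 data holds only under Section 4 and Table IV.

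A third tempting step is to count how many of the six hypotheses lose their data. The documents do not support a firm count. They do not say which endpoints are primary or secondary, the outcomes named for the ANOVA are examples, and the retention test names none.

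The defense does not settle the duration. Section 1 gives the same 12 + 2 design as Section 14, so this is not an isolated slip in one number, and the functional wording fits either design.

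**Conclusion.** The concern holds as an internal inconsistency that needs correcting before conduct or analysis relies on it. Two coherent designs coexist, 12 + 2 weeks and 6 + 2 weeks. They differ two-fold in planned exposure (672 v 336 hours) and in whether week 8 is on or off treatment. Under the operational schedule, the between-group ANOVA and the reference of the retention t-test have no data at their stated week. Analyses that depend on the end of treatment are also affected; the sample size is not.

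Taking 6 weeks as the working reading is a judgment. It rests on Section 4, Table IV and Hypothesis 4 agreeing with one another on visit or assessment timing. The documents do not say which duration is intended, so the sponsor must confirm it. The hours assume full nightly use as prescribed.

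**What to change.** **Default, unless the sponsor confirms 12 weeks:**

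- Section 1: state 6 weeks of treatment plus 2 weeks of retention, and replace the monthly balance assessments with two-weekly ones, as in Specific Aim 1.
- Section 14: set the end-of-treatment between-group comparison at week 6, and the retention paired t-test as week 8 v week 6.
- Limit the retention test to outcomes measured at both visits: balance, gait, neuropathy, pain VAS and vascular measures. Exclude SF-12. Include activity monitoring only if the every-visit schedule of Hypothesis 5 is kept over Table IV.
- Table IV: align the fall log's 4-week period with the 8-week schedule.

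This costs wording only, with no added visits.

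**If 12 weeks is intended:** Section 4 and Table IV must schedule week 12 (end of treatment) and week 14 (retention), relabel week 8 as on treatment, and move SF-12 and activity monitoring to week 12. The retention test becomes week 14 v week 12 for outcomes measured at both. The cost is 6 more weeks of device use per participant, plus visits that depend on the interval chosen (weeks 10 and 14 are inferred):

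- Monthly {0, 4, 8, 12, 14}: 5 visits, so 5 − 5 = 0 extra. The two-weekly comparisons in Section 14 would then have to change.
- Two-weekly {0, 2, 4, 6, 8, 10, 12, 14}: 8 visits, so 8 − 5 = 3 extra each, or 3 × 80 = 240 in total before dropout.
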